12 INSTITUTIONAL REVIEW

This study must be reviewed and approved by an appropriate Institutional Review Board (IRB) or Independent Ethics Committee (IEC). A copy of the letter indicating IRB/IEC approval must be provided to Glaukos (or designee) prior to study initiation. Updates must be provided to the IRB/IEC by the investigator at least annually or as required by the IRB/IEC.

CLINICAL PROTOCOL

Date:

September 18, 2019

Protocol No.:

IDOS-402-IVIV

14 STATEMENT OF COMPLIANCE

This study will be conducted in compliance with the protocol, good clinical practices (GCP), and all applicable laws and regulations.

The clinical investigator must maintain all information supplied by Glaukos in confidence, and when this information is submitted to an institutional review board (IRB), independent ethics committee (IEC) or another group, it will be submitted with a designation that the material is confidential.

The clinical investigator must ensure that all persons assisting with the trial are adequately informed about the protocol, the investigational product(s), and their trial-related duties and functions.

15 RECORD KEEPING

15.1 Source Documents

The clinical investigator must maintain detailed source documents on all study subjects. Source documents include investigator subject study files, subject medical records, hospital charts, clinic charts, as well as the results of diagnostic tests (e.g., laboratory tests, visual field test printouts).

CLINICAL PROTOCOL

Date: September 18, 2019	Protocol No.: IDOS-402-IVIV
-----------------------------	--------------------------------

The following minimum information should be entered into the subject's medical record:

- The date the subject completed the screening visit and the subject number assigned
- The study protocol number and the name of Glaukos
- The date that informed consent was obtained including the version number and date of the consent form used
- Evidence that the subject meets study eligibility requirements (e.g., medical history, study procedures and/or evaluations)
- The dates of all study related subject visits
- Evidence that required procedures and/or evaluations were completed
- Use of any concurrent medications
- Documentation of study medication accountability, including a copy of study medication labels
- Occurrence and status of any adverse events
- The date the subject exited the study, and a notation as to whether the subject completed the study or was discontinued, including the reason for discontinuation

15.2 Data Collection

The clinical investigator must maintain detailed records on all enrolled subjects. Data for enrolled subjects will be collected with an electronic data capture system. The electronic database, which is Title 21 CFR Part 11 compliant, will be managed by a data management vendor. Access to the database will be granted to authorize study personnel based on their role after training; and the access will be password-protected. The data clarification process will be managed within the electronic data capture system by either system-generated or manually generated electronic queries. Accuracy of data will be verified by source data verification at regular intervals, and all corrections to data will be made in the database. CRF forms are completed for all enrolled subjects, regardless of their final study status (e.g., subject discontinuation, study termination).

15.3 Study Supply Accountability

The principal investigator is responsible for ensuring that study material, including investigational product, is logged and placed in inventory upon receipt of the clinical supplies and that the clinical study supplies are stored as instructed. The receipt of clinical supplies should be completed, signed, and returned as directed by Glaukos (or designee). A copy must be maintained at the site for the investigator's records. The principal investigator will keep a

CLINICAL PROTOCOL

Date: September 18, 2019	Protocol No.: IDOS-402-IVIV
-----------------------------	--------------------------------

current record of the inventory and dispensing of all study medications. This record will be made available to the Glaukos monitor (or designee) for the purpose of accounting for all clinical supplies. Any significant discrepancy and/or deficiency must be recorded with an explanation. All supplies sent to the investigator must be accounted for and in no case will study medications be used in any unauthorized situation. It is the responsibility of the principal investigator to return or destroy any used and unused supplies to the Glaukos monitor (or designee) at the conclusion of the study.

15.4 Record Retention

All records relating to the conduct of this study are to be retained by the investigator until notified by Glaukos that the records may be destroyed.

The investigator will allow representatives of Glaukos' monitoring team (or designee), the governing institutional review board, the Food and Drug Administration (FDA), and other applicable regulatory agencies to inspect all study records, CRFs, and corresponding portions of the subject's office and/or hospital medical records at regular intervals throughout the study. These inspections are for the purpose of verifying adherence to the protocol, completeness, and exactness of the data being entered onto the CRF, and compliance with FDA or other regulatory agency regulations.

CLINICAL PROTOCOL

Date:
September 18, 2019

Protocol No.:
IDOS-402-IVIV

1 Only required if Corrected VA (ETDRS) has decreased by 2 or more lines (≥ 10 letters) from Visit 1 (Screening).

2 Second Operative / Exchange is done AFTER collecting the anterior chamber aqueous humor sample and all assessments

3 Pre-exchange exam to occur within 10 days prior to Visit 7 (Second Operative / Exchange Exam)

Operative Visits are in Red

CLINICAL PROTOCOL

Date:
September 18, 2019

Protocol No.:
IDOS-402-IVIV

APPENDIX B: SCHEDULE OF VISITS & MEASUREMENTS: Group 3

(3 months from 1st Implant Insertion to 2nd Implant Insertion, [REDACTED])

Parameter	Screening	Operative Day 0	Day 1	Day 10, 10 days ± 3	Week 4, 28 days ± 3	Pre-Exchange ³	Month 3, 91 days ± 14	Day 1 Post Exchange (PE)	Day 10 PE, 10 days ± 3	Week 4 PE, 28 days ± 3
Visit Number	1	2	3	4	5	6	7	8	9	10
Informed Consent	x									
Pregnancy Test	x									
Demographics, Medical/Ocular History	x	x								
Concomitant Medication Assessment	x	x	x	x	x	x	x	x	x	x
Adverse Event Assessment		x	x	x	x	x	x	x	x	x
Corrected VA (ETDRS)					x	x				x
Manifest Refraction & BSCVA (ETDRS)	x			x ¹	x ¹					x ¹
Pinhole VA (Snellen)			x	x				x	x	
Slit Lamp Exam	x		x	x	x	x		x	x	x
IOP	x		x	x	x	x		x	x	x
Gonioscopy	x				x	x				x
Pachymetry	x									
Dilated Fundus Exam and Nerve Assessment, Vertical C/D ratio	x									
Aqueous Humor Sample (AC Tap)							x			
Operative Procedure and Surgical Assessments		x					x ²			

1 Only required if Corrected VA (ETDRS) has decreased by 2 or more lines (≥ 10 letters) from Visit 1 (Screening).

2 Second Operative / Exchange is done AFTER collecting the anterior chamber aqueous humor sample and all assessments

3 Pre-exchange exam to occur within 10 days prior to Visit 7 (Second Operative / Exchange Exam)

Operative Visits are in Red

CLINICAL PROTOCOL

Date:
September 18, 2019

Protocol No.:
IDOS-402-IVIV

APPENDIX C: SCHEDULE OF VISITS & MEASUREMENTS: Group 6

(6 months from 1st Implant Insertion to 2nd Implant Insertion, [REDACTED])

Parameter	Screening	Operative Day 0	Day 1	Day 10, 10 days ± 3	Week 4, 28 days ± 3	Pre-Exchange ³	Month 6, 182 days ± 14	Day 1 Post Exchange (PE)	Day 10 PE, 10 days ± 3	Week 4 PE, 28 days ± 3
Visit Number	1	2	3	4	5	6	7	8	9	10
Informed Consent	x									
Pregnancy Test	x									
Demographics, Medical/Ocular History	x	x								
Concomitant Medication Assessment	x	x	x	x	x	x	x	x	x	x
Adverse Event Assessment		x	x	x	x	x	x	x	x	x
Corrected VA (ETDRS)					x	x				x
Manifest Refraction & BSCVA (ETDRS)	x			x ¹	x ¹					x ¹
Pinhole VA (Snellen)			x	x				x	x	
Slit Lamp Exam	x		x	x	x	x		x	x	x
IOP	x		x	x	x	x		x	x	x
Gonioscopy	x				x	x				x
Pachymetry	x									
Dilated Fundus Exam and Nerve Assessment, Vertical C/D ratio	x									
Aqueous Humor Sample (AC Tap)							x			
Operative Procedure and Surgical Assessments		x					x ²			

1 Only required if Corrected VA (ETDRS) has decreased by 2 or more lines (≥ 10 letters) from Visit 1 (Screening).

2 Second Operative / Exchange is done AFTER collecting the anterior chamber aqueous humor sample and all assessments

3 Pre-exchange exam to occur within 10 days prior to Visit 7 (Second Operative / Exchange Exam)

Operative Visits are in Red

CLINICAL PROTOCOL

Date:
September 18, 2019

Protocol No.:
IDOS-402-IVIV

APPENDIX D: SCHEDULE OF VISITS & MEASUREMENTS: Group 24

(24 months from 1st Implant Insertion to 2nd Implant Insertion, [REDACTED])

Parameter	Screening	Operative Day 0	Day 1	Day 10, 10 days ± 3	Week 4, 28 days ± 3	Month 6, 182 days ± 14	Month 12, 365 days ± 14	Month 18, 547 days ± 14	Pre-Exchange ³	Month 24, 730 days ± 14	Day 1 Post Exchange (PE)	Day 10 PE, 10 days ± 3	Week 4 PE, 28 days ± 3
Visit Number	1	2	3	4	5	5.1	5.2	5.3	6	7	8	9	10
Informed Consent	x												
Pregnancy Test	x												
Demographics, Medical/Ocular History	x	x											
Concomitant Medication Assessment	x	x	x	x	x	x	x	x	x	x	x	x	x
Adverse Event Assessment		x	x	x	x	x	x	x	x	x	x	x	x
Corrected VA (ETDRS)					x	x	x	x	x				x
Manifest Refraction & BSCVA (ETDRS)	x				x ¹	x ¹	x ¹	x ¹	x ¹				x ¹
Pinhole VA (Snellen)			x	x							x	x	
Slit Lamp Exam	x		x	x	x	x	x	x	x		x	x	x
IOP	x		x	x	x	x	x	x	x		x	x	x
Gonioscopy	x				x	x	x	x	x				x
Pachymetry	x												
Dilated Fundus Exam and Nerve Assessment, Vertical C/D ratio	x												
Aqueous Humor Sample (AC Tap)										x			
Operative Procedure and Surgical Assessments		x								x ²			

1 Only required if Corrected VA (ETDRS) has decreased by 2 or more lines (≥ 10 letters) from Visit 1 (Screening).

2 Second Operative / Exchange is done AFTER collecting the anterior chamber aqueous humor sample and all assessments

3 Pre-exchange exam to occur within 10 days prior to Visit 7 (Second Operative / Exchange Exam)

Operative Visits are in Red

CLINICAL PROTOCOL

Date:
September 18, 2019

Protocol No.:
IDOS-402-IVIV

APPENDIX E: SCHEDULE OF VISITS & MEASUREMENTS: Group 21

(21 months from 1st Implant Insertion to 2nd Implant Insertion, [REDACTED])

Parameter	Screening	Operative Day 0	Day 1	Day 10, 10 days ± 3	Week 4, 28 days ± 3	Month 6, 182 days ± 14	Month 12, 365 days ± 14	Month 18, 547 days ± 14	Pre-Exchange ³	Month 21, 637 days ± 14	Day 1 Post Exchange (PE)	Day 10 PE, 10 days ± 3	Week 4 PE, 28 days ± 3
Visit Number	1	2	3	4	5	5.1	5.2	5.3	6	7	8	9	10
Informed Consent	x												
Pregnancy Test	x												
Demographics, Medical/Ocular History	x	x											
Concomitant Medication Assessment	x	x	x	x	x	x	x	x	x	x	x	x	x
Adverse Event Assessment		x	x	x	x	x	x	x	x	x	x	x	x
Corrected VA (ETDRS)					x	x	x	x	x				x
Manifest Refraction & BSCVA (ETDRS)	x			x ¹	x ¹	x ¹	x ¹	x ¹					x ¹
Pinhole VA (Snellen)			x	x							x	x	
Slit Lamp Exam	x		x	x	x	x	x	x	x		x	x	x
IOP	x		x	x	x	x	x	x	x		x	x	x
Gonioscopy	x				x	x	x	x	x				x
Pachymetry	x												
Dilated Fundus Exam and Nerve Assessment, Vertical C/D ratio	x												
Aqueous Humor Sample (AC Tap)										x			
Operative Procedure and Surgical Assessments		x								x ²			

1 Only required if Corrected VA (ETDRS) has decreased by 2 or more lines (≥ 10 letters) from Visit 1 (Screening).

2 Second Operative / Exchange is done AFTER collecting the anterior chamber aqueous humor sample and all assessments

3 Pre-exchange exam to occur within 10 days prior to Visit 7 (Second Operative / Exchange Exam)

Operative Visits are in Red

CLINICAL PROTOCOL

Date:
September 18, 2019

Protocol No.:
IDOS-402-IVIV

APPENDIX F: SCHEDULE OF VISITS & MEASUREMENTS: Group 18

(18 months from 1st Implant Insertion to 2nd Implant Insertion, [REDACTED])

Parameter	Screening	Operative Day 0	Day 1	Day 10, 10 days ± 3	Week 4, 28 days ± 3	Month 6, 182 days ± 14	Month 12, 365 days ± 14	Pre-Exchange ³	Month 18, 547 days ± 14	Day 1 Post Exchange (PE)	Day 10 PE, 10 days ± 3	Week 4 PE, 28 days ± 3
Visit Number	1	2	3	4	5	5.1	5.2	6	7	8	9	10
Informed Consent	x											
Pregnancy Test	x											
Demographics, Medical/Ocular History	x	x										
Concomitant Medication Assessment	x	x	x	x	x	x	x	x	x	x	x	x
Adverse Event Assessment		x	x	x	x	x	x	x	x	x	x	x
Corrected VA (ETDRS)					x	x	x	x				x
Manifest Refraction & BSCVA (ETDRS)	x			x ¹	x ¹	x ¹	x ¹					x ¹
Pinhole VA (Snellen)			x	x						x	x	
Slit Lamp Exam	x		x	x	x	x	x	x		x	x	x
IOP	x		x	x	x	x	x	x		x	x	x
Gonioscopy	x				x	x	x	x				x
Pachymetry	x											
Dilated Fundus Exam and Nerve Assessment, Vertical C/D ratio	x											
Aqueous Humor Sample (AC Tap)									x			
Operative Procedure and Surgical Assessments		x							x ²			

1 Only required if Corrected VA (ETDRS) has decreased by 2 or more lines (≥ 10 letters) from Visit 1 (Screening).

2 Second Operative / Exchange is done AFTER collecting the anterior chamber aqueous humor sample and all assessments

3 Pre-exchange exam to occur within 10 days prior to Visit 7 (Second Operative / Exchange Exam)

Operative Visits are in Red

CLINICAL PROTOCOL

Date:
September 18, 2019

Protocol No.:
IDOS-402-IVIV

APPENDIX G: SCHEDULE OF VISITS & MEASUREMENTS: Group 15

(15 months from 1st Implant Insertion to 2nd Implant Insertion, [REDACTED])

Parameter	Screening	Operative Day 0	Day 1	Day 10, 10 days ± 3	Week 4, 28 days ± 3	Month 6, 182 days ± 14	Month 12, 365 days ± 14	Pre-Exchange ³	Month 15, 456 days ± 14	Day 1 Post Exchange (PE)	Day 10 PE, 10 days ± 3	Week 4 PE, 28 days ± 3
Visit Number	1	2	3	4	5	5.1	5.2	6	7	8	9	10
Informed Consent	x											
Pregnancy Test	x											
Demographics, Medical/Ocular History	x	x										
Concomitant Medication Assessment	x	x	x	x	x	x	x	x	x	x	x	x
Adverse Event Assessment		x	x	x	x	x	x	x	x	x	x	x
Corrected VA (ETDRS)					x	x	x	x				x
Manifest Refraction & BSCVA (ETDRS)	x			x ¹	x ¹	x ¹	x ¹					x ¹
Pinhole VA (Snellen)			x	x						x	x	
Slit Lamp Exam	x		x	x	x	x	x	x		x	x	x
IOP	x		x	x	x	x	x	x		x	x	x
Gonioscopy	x				x	x	x	x				x
Pachymetry	x											
Dilated Fundus Exam and Nerve Assessment, Vertical C/D ratio	x											
Aqueous Humor Sample (AC Tap)									x			
Operative Procedure and Surgical Assessments		x							x ²			

1 Only required if Corrected VA (ETDRS) has decreased by 2 or more lines (≥ 10 letters) from Visit 1 (Screening).

2 Second Operative / Exchange is done AFTER collecting the anterior chamber aqueous humor sample and all assessments

3 Pre-exchange exam to occur within 10 days prior to Visit 7 (Second Operative / Exchange Exam)

Operative Visits are in Red

CLINICAL PROTOCOL

Date: September 18, 2019	Protocol No.: IDOS-402-IVIV
-----------------------------	--------------------------------

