6.2 Eligibility Requirements

6.2.1 INCLUSION CRITERIA

6.2.1.1 Visit 1 (Screening) Inclusion Criteria

At Visit 1 (Screening), all subjects must meet the following criteria:

- 1) Subject status as follows:
 - a. male or female, 18 years of age or older
 - b. able and willing to attend scheduled follow-up exams for the duration of the study
 - c. able and willing to provide written informed consent on the IRB/IEC-approved Informed Consent Form

Both eyes may be assessed at Visit 1 (Screening).

- 2) Diagnosis of either OAG (i.e. primary, pseudoexfoliation, or pigmentary glaucoma) or OHT.

All subjects must meet the rest of the following criteria:

- 3) Zero to three topical IOP lowering medications at the time of Visit 1 (Screening) exam. Combination medications (e.g., Cosopt®, Combigan®) are to be counted as two medications.
- 4) Best spectacle corrected visual acuity of 16 letters or more correctly read at 4 meters or better in each eye.
- 5) Angle anatomy defined as follows:
 - a. open angle as defined by Shaffer grade ≥ 3 at slit-lamp at the planned implantation site
 - b. normal anatomy as determined by gonioscopy
 - c. absence of peripheral anterior synechia (PAS), rubeosis or other angle abnormalities that could impair proper placement of the product at the planned implantation site.
- 6) Lens status as follows:
 - a. Phakic, with crystalline lens that does not have visually significant cataract expected to require cataract surgery for the duration of the study, OR
 - b. Pseudophakic, with uncomplicated cataract surgery performed > 90 days prior and with implanted posterior chamber IOL fixated in the capsular bag
- 7) Central corneal thickness ≥ 440 microns and ≤ 620 microns.

CLINICAL PROTOCOL

Date:
September 18, 2019

Protocol No.:
IDOS-402-IVIV

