6.2.2 EXCLUSION CRITERIA

6.2.2.1 Visit 1 (Screening) Exclusion Criteria

Subjects who meet any of the following criteria in the study eye at Visit 1 (Screening) are not eligible to participate in the study:

- 1) Glaucoma status as follows:
 - a. Traumatic, uveitic, neovascular, or angle-closure glaucoma; or glaucoma associated with vascular disorders
 - b. Functionally significant visual field loss, including severe nerve fiber bundle defects
 - c. Prior incisional glaucoma surgery
- 2) Corneal status as follows:
 - a. any active inflammation or edema (e.g., keratitis, keratoconjunctivitis, kerato-uveitis)
 - b. clinically significant dystrophy (e.g., bullous keratopathy, Fuch's dystrophy)
 - c. clinically significant guttata
 - d. significant scarring or irregularities (including scars from prior corneal surgery such as PKP, RK, etc.), during the course of the study, that may interfere with IOP measurement reliability
 - e. anticipated surgery of any type (including LASIK, LASEK, PRK, etc.), during the course of the study, that may interfere with IOP measurement reliability
 - f. opacities or disorders that would inhibit visualization of the nasal angle.
- 3) Congenital or traumatic cataract (except Mittendorf dots).
- 4) Choroidal detachment, effusion, choroiditis, neovascularization, or any active choroidopathy.
- 5) Retinal or optic nerve disorders, either degenerative or evolutive, that are not associated with the existing glaucoma condition, including proliferative diabetic retinopathy, central retinal artery occlusion, central retinal vein occlusion, wet age-related macular degeneration, advanced dry age-related macular degeneration, (e.g., presence of numerous large drusen associated with disturbance to or elevation of the retinal pigment epithelium), significant retinal pigment epithelial changes or optic atrophy.

CLINICAL PROTOCOL

Date:
September 18, 2019

Protocol No.:
IDOS-402-IVIV

- 6) Other ocular status as follows:
 - a. clinically significant sequelae from trauma (e.g., chemical burns, blunt trauma, etc.)
 - b. history or chronic ocular inflammatory disease or presence of active ocular inflammation (e.g., uveitis, iritis, iridocyclitis, retinitis, ocular herpes)
 - c. any pathology for which, in the investigator's judgment, the following would be either at risk or contraindicated:
 - i. implantation of Travoprost Intraocular Implant
 - ii. compliance to elements of the study protocol (e.g., ophthalmic examinations, follow-up visits).

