- 7) Fellow eye status as follows:
 - a. fellow eye actively enrolled in this trial or any other clinical trial.
- 8) Subject status as follows:
 - a. pregnant or planning to become pregnant during the course of the study
 - b. uncontrolled systemic disease (e.g., diabetes, hypertension) that could compromise participation in the study
 - c. current participation in any study, or participation within 30 calendar days of Visit 1 (Screening)
 - d. immunodeficiency conditions
 - e. change in an existing chronic systemic therapy that could substantially affect IOP or the study outcomes within 30 days prior to Visit 1 (Screening), or anticipated change in such therapy during the study duration
 - f. anticipated to need a topical prostaglandin analogue medication for the duration of the study
 - g. known allergy, hypersensitivity or contraindication to the study medications or their components, namely prostaglandin analogues
 - h. any ocular disease or condition that in the opinion of the investigator or Medical Monitor may put the subject at significant risk, may confound the study results, or may interfere significantly with the subject's participation in the study. In addition, the investigator or the Medical Monitor may declare any subject ineligible for any sound medical reason.

CLINICAL PROTOCOL

Date: September 18, 2019	Protocol No.: IDOS-402-IVIV
-----------------------------	--------------------------------

- 9) The inability to visualize the implantation site via surgical gonioscopy.

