6.3.3 PREOPERATIVE PROCEDURES

6.3.3.1 Visit 1 (Screening)

- 1) Written informed consent.
- 2) Assign subject number.
- 3) Demographics, medical and surgical history, current ocular and systemic conditions, prescription medications, and medications known or suspected to lower IOP.
- 4) A pregnancy test (if applicable) may be administered at any time during this visit.

CLINICAL PROTOCOL

Date:
September 18, 2019

Protocol No.:
IDOS-402-IVIV

- 5) Measure best spectacle corrected visual acuity through manifest refraction (ETDRS) in each eye.
- 6) Perform slit-lamp biomicroscopy (including crystalline lens).
- 7) Measure IOP (can be measured at any time) and record the time.
- 8) Pachymetry.
- 9) Perform a gonioscopic examination.
- 10) Perform a dilated ophthalmoscopy/fundus examination.
- 11) Assess optic nerve abnormality (ophthalmoscopy).
- 12) Assess vertical C/D ratio.
- 13) Review screening inclusion and exclusion criteria. Do not continue screening any subject who does not meet the screening eligibility requirements.

If the subject is qualified:

- 1) Schedule the subject for Visit 2 (First Operative Day 0).
- 2) [REDACTED]
- 3) Advise the subject to discontinue taking their topical hypotensive medication beginning the morning of visit 2 (First Operative Day)
[REDACTED]

If the subject is ineligible for the study, complete the appropriate CRF.

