6.3.4.7 Visit 7 (Second Operative / Exchange Exam)

Depending on the cohort, the subject may have their Visit 7 (Second Operative / Exchange Exam) occur on one of the following visits (please see **APPENDIX A-G: SCHEDULE OF VISITS & MEASUREMENTS):**

CLINICAL PROTOCOL

Date:
September 18, 2019

Protocol No.:
IDOS-402-IVIV

(Month 12, 365 days ± 14)

(Month 3, 91 days ± 14)

(Month 6, 182 days ± 14)

(Month 24, 730 days ± 14)

(Month 21, 637 days ± 14)

(Month 18, 547 days ± 14)

(Month 15, 456 days ± 14)

- 1) Update subject's medical status and concomitant medications.
- 2) Assess study eye adverse events.
- 3) Prepare subject for surgery.
- 4) [REDACTED]

The following steps will be performed in the Operating Room:

- 5) Visually confirm Shaffer grade angle and target implant location.
- 6) Collect an anterior chamber aqueous humor sample (AC tap).
Please follow instructions in the procedure manual.

After collecting the AC Tap and performing all assessments:

- 7) Obtain a treatment kit.
- 8) Administer anesthetic [REDACTED]
- 9) Perform second surgery (Exchange).
- 10) Collect the first implant for shipment back to sponsor.
- 11) Record clinical data from the surgical procedure on the Second Operative CRF, noting study eye intra-operative AEs and post-operative AEs.
- 12) Schedule the subject to return for Visit 8 (Day 1 Post Exchange).

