7 EXTENT OF EXPOSURE AND TREATMENT COMPLIANCE

All subjects will be implanted with a Travoprost Intraocular Implant. All subjects will then be implanted with a second Travoprost Intraocular Implant (at either month 12, 3, 6, 24, 21, 18, or 15, depending on cohort assignment) to exchange with the first one that will be explanted. All subjects will be followed for 4 weeks following the exchange procedure for a total duration of 4 to 25 months.

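### The only scheduled pregnancy test is at Screening; for women to whom it applies, none is scheduled before the second implant, 77 to 744 days after the first

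*Protocol*

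**What the plan says.** Enrolment is open to subjects who are "male or female, 18 years of age or older", with no upper age limit (Protocol 6.2.1.1). Exclusion 8a in 6.2.2.1 bars a subject who is "pregnant or planning to become pregnant during the course of the study". The list it belongs to opens: "Subjects who meet any of the following criteria in the study eye at Visit 1 (Screening) are not eligible to participate in the study".

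The Visit 1 procedures (Protocol 6.3.3.1) state: "A pregnancy test (if applicable) may be administered at any time during this visit". In each of Appendices A to G the row labelled "Pregnancy Test" carries one mark, under Screening. The copies in SAP section 11 and in section 7 of the data analysis plan show the same. None of these schedules marks a test at Visit 2, 6 or 7.

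Protocol section 7 says: "All subjects will then be implanted with a second Travoprost Intraocular Implant". The exchange takes place at Visit 7. The shortest cohort is timed at "Month 3, 91 days ± 14" (6.3.4.7), and the Appendix D schedule is headed "24 months from 1st Implant Insertion to 2nd Implant Insertion".

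**The concern.** The protocol treats pregnancy status as relevant to entering a study of this implant: it excludes on it and schedules a test for it. It then places a second implant months to two years later, and the schedule does not repeat the check. The wording of 8a looks across the whole study, which lasts 4 to 25 months, while the only scheduled means of establishing the fact sits at its start.

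This is a patient-safety point. A woman who became pregnant after Screening, and did not know it or did not report it, could receive the second implant with the plan followed exactly. Section 9.1 counts a congenital anomaly or birth defect as a serious outcome. Without pregnancy status at exchange, the study could not reliably identify which second implantations took place during a pregnancy.

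**Working it through.** **Timing of the second implant.** Protocol 6.3.4.7 gives a nominal day for each of the seven durations, each ±14 days. As a check, nominal day = months × 365/12. The window is the stated day − 14 to the stated day + 14.

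| Month | Stated day | Months × 365/12 | Window (days after first implant) |
|---|---|---|---|
| 3 | 91 | 91.25 | 77 to 105 |
| 6 | 182 | 182.5 | 168 to 196 |
| 12 | 365 | 365 | 351 to 379 |
| 15 | 456 | 456.25 | 442 to 470 |
| 18 | 547 | 547.5 | 533 to 561 |
| 21 | 637 | 638.75 | 623 to 651 |
| 24 | 730 | 730 | 716 to 744 |

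The stated days are reproduced to within 2 days. The outer limits are 91 − 14 = 77 and 730 + 14 = 744 days. These are the ends of seven separate windows, not one continuous span. They count from the first implant. The interval from the test is longer, because Screening precedes Day 0 and section 3 limits that gap only by requiring a separate day.

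**Number of women concerned.** The documents do not give it, and the readable text does not define to whom the test applies. Assuming 1% to 5% of the 210 planned subjects: 0.01 × 210 = 2.1 and 0.05 × 210 = 10.5, so about 2 to 10 women. The 1% to 5% is an illustration with no support in the documents.

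**Whether another provision closes the gap.**
- Visits 6 and 7 (6.3.4.6 and 6.3.4.7) include an update of medical status and medications. This may bring out a known pregnancy but is not a test.
- Step 4 of Visit 7 is redacted. The schedule rows are readable and show no test at that visit.
- Section 6.2.3.2 allows exit for a condition that could make continued participation harmful. It does not name pregnancy and gives no means of finding one.
- Section 9 asks in one place for events in the study eye that are judged related, and in another for any clinically significant change whatever its cause. Whether a pregnancy would be recorded is therefore unclear.
- No readable section states what happens if pregnancy arises after the first implant.

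**The case against.** The strongest reply is that the documents agree on where the test falls. The exclusions apply at Visit 1, 8a concerns current pregnancy or an intention at that point, the Visit 1 text places the test there, and every schedule marks it there. An entry criterion does not promise later monitoring. This stands: there is no direct contradiction, and a reader who infers that 8a is itself a rule for pregnancy arising during follow-up goes beyond its text. What remains is that a criterion worded for the study's duration has one scheduled check, before the first of two implantations.

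A reader might also infer that the second implant of every subject is affected, that is 210 of 420 implantations (2 × 210). That does not follow. Men are eligible and the test is conditional, so those figures count many subjects for whom no test applies.

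A third tempting reading is that the permissive verb in 6.3.3.1 makes the test optional and so conflicts with the schedule's mark. The verb plausibly governs only the time within the visit; the IOP item in the same list is phrased in a similar way.

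Two further replies limit the point without removing it. No test is marked at Visit 2 either, so the contrast is between entry and exchange, not between two operating days. And redacted steps, or the procedure manual cited at Visit 7, could hold pregnancy instructions. For both reasons the finding is that no test is scheduled, not that pregnancy status goes wholly unchecked.

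**Conclusion.** The point holds in a limited form. For women to whom the test applies, the readable plan schedules none between Screening and the second implantation, which falls 77 to 744 days after the first depending on cohort. It is a gap between the reach of exclusion 8a and the schedule. The number affected is unknown and probably small: about 2 to 10 women under the assumed 1% to 5%.

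The conclusion rests on the schedule rows being complete as printed and on no redacted or separate instruction supplying the check. It should be corrected because the potential harm is serious and the amendment is light. It has no bearing on the sample size, which is not power-based.

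**What to change.** Reconcile exclusion 8a (6.2.2.1), the Visit 1 text (6.3.3.1) and the pregnancy-test row of Appendices A to G, together with the copies in SAP section 11 and data analysis plan section 7. After reconciliation the schedule should state how pregnancy status is established for applicable subjects before the second implantation as well as at entry, and the text should say how 8a is to be read after entry. The pre-exchange exam at Visit 6 already exists, within 10 days before Visit 7, and is available for this purpose. If a redacted step or the procedure manual already covers the matter, the schedule should point to it.

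The choice of test, its timing and the action on a positive result are for the sponsor and investigator.

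The cost is one schedule row with its copies, a short clarification, and a repeat for a few subjects of a check already in the protocol. A few exchanges might be delayed or missed. With 15 subjects per cohort (data analysis plan 2.3), one missed exchange removes 1/15, about 7%, of a cohort's explants and aqueous samples, although section 6.2.3 allows subjects who leave early to be replaced.
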